### **6.4. Secondary outcomes**

1. The baseline to 90 day change in cardiac arrhythmia detection (i.e. presence/absence) of a smart phone based event recorder compared with standard care only shall be analysed using comparison of proportions test.
2. A log-rank test and Kaplan-Meier curves shall be used to examine if the smartphone recorder has an effect on time to first detection of symptomatic rhythm up to 90 days versus standard care only.
3. A log-rank test and Kaplan-Meier curves shall be used to examine if the smartphone recorder has an effect on time to first detection of cardiac arrhythmia rhythm up to 90 days versus standard care only.

4. The number of participants treated (or planned for treatment) for cardiac arrhythmia in those using a smart phone based event recorder versus standard care only shall be analysed using a comparison of proportions test.
5. Participant satisfaction questionnaire responses shall be compared between study arms using  $\chi^2$  test(s) (and  $\chi^2$  test(s) for trend if appropriate). A similar analysis shall be performed for participant compliance questionnaire responses.
6. The number of participants recorded for each of the following shall be collated. If appropriate and numbers allow, a two-sample t-test (or non-parametric equivalent as appropriate) shall be used to compare study arms where the outcome of interest is continuous. However if the numbers are to be treated as categorical then a  $\chi^2$  test (and if appropriate,  $\chi^2$  test for trend) shall be used to compare study arms:
  - Number of ED presentations (except index visit) due to palpitations/pre-syncope.
  - Number of inpatient hospital days (over all admissions) due to palpitations/pre-syncope.
  - Number of outpatient presentations due to palpitations/pre-syncope.
  - Number of GP presentations due to palpitations/pre-syncope (via phone follow-up).
  - Number of TRAK ECGs due to palpitations/pre-syncope.

A comparison of the overall cost-effectiveness of the smart phone based event recorder and standard care shall be provided using a two-sample t-test (or non-parametric equivalent as appropriate) between study arms. The costing scope will include primary care, secondary care and community NHS costs which shall be provided separately by the CI for analysis.

7. The number of participants recording at least one serious outcome at 90 days in those using a smart phone based event recorder compared to standard care only shall be examined by a comparison of proportions test. Following on from this the number of serious outcomes at 90 days between the two study arms shall be examined using a  $\chi^2$  test (and  $\chi^2$  test for trend if appropriate).

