### **6.2 STUDY ASSESSMENTS**

Potentially eligible ED and AMU participants will be identified and assessed for study inclusion by the attending clinician. Written consent will be taken and participants will have a Case Report Form (CRF) completed and a 12-lead ECG taken if not already performed by the clinical team.

All STUDY arm participants will be given an AliveCor Heart Monitor and trained in the use of the device and app in the ED or AMU by the research team.

CONTROL arm participants will receive no other intervention.

Participants in both groups will be admitted, referred or discharged by the treating clinician according to current local hospital protocols.

Participants in both groups will be followed up at 90 days through hospital record systems (paper or electronic depending on local policy), GP records and by telephone by the local study team. Participants will also be asked to complete a standardised written questionnaire and will receive a follow-up telephone call from the local study team enquiring about symptoms and contact with medical services. Participants will also be asked about satisfaction and compliance with the heart monitor.

Participants allocated to the Study arm may be contacted by telephone by the local research team shortly after randomisation in the event of them requiring further training or setting up of the device. For example, this may be necessary if a participant does not have their app store password with them in the ED or AMU. If a local electronic patient record system is available, then a research alert will be placed on this stating that the participant has consented to be part of the IPED study.

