### **2.2. Study endpoints**

The primary endpoint is the symptomatic rhythm detection rate of a smart phone based event recorder (AliveCor Monitor) for symptomatic rhythm detection at 90 days versus standard care for participants presenting to the ED with palpitations and pre-syncope with no obvious cause in the ED.

The secondary endpoints are:

1. Symptomatic rhythm detection rate of a smart phone based event recorder for cardiac arrhythmia detection at 90 days versus standard care.
2. Time to detection of symptomatic rhythm using a smart phone based event recorder versus standard care.
3. Time to detection of cardiac arrhythmia rhythm using a smart phone based event recorder versus standard care.
4. Number of participants treated or (planned for treatment) for cardiac arrhythmia in participants using a smart phone based event recorder versus standard care.

5. Participant satisfaction and monitor compliance.
6. Cost effectiveness analysis.
7. Serious outcomes at 90 days: all cause death and major adverse cardiac events (myocardial infarction, life-threatening arrhythmia, insertion of a pacemaker or internal cardiac defibrillator, insertion of pacing wire).

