### **4.2.2. Follow up assessments**

Participants in both groups will be followed up at 90 days through hospital record systems (paper or electronic depending on local policy), GP records and by telephone by the local study team. Participants will also be asked to complete a standardised written questionnaire and will receive a follow-up telephone call from the local study team enquiring about symptoms and contact with medical services. Study arm participants will also be asked about satisfaction and compliance with the heart monitor.

Participants allocated to the Study arm may be contacted by telephone by the local research team shortly after randomisation in the event of them requiring further training or setting up of the device.

If a participant allocated to the Study arm gets an episode of palpitations or pre-syncope and is able to record an AliveCor Heart Monitor ECG during the episode, the participant will email the ECG recorded by the AliveCor app directly to the co-ordinating Edinburgh research team at a convenient time to the participant and to a secure nhs.net email address.

The co-ordinating Edinburgh research team will review the ECG and will contact the local study team to arrange follow-up if required. If specialist follow-up of the ECG tracing is not required then the local study team will write to the participant informing them of this and ask them to arrange follow up with their general practitioner who will be contacted with the report. The participant and GP will not be contacted further should participants record other similar ECGs that similarly do not require specialist follow-up.

If the participant records a serious significant arrhythmia during the study period, the local study team will alert the participant immediately by telephone, and refer them urgently to their local Emergency Department or cardiac electrophysiology service (as per local protocol).

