### **4.2.3. Participant symptom diary, satisfaction and compliance**

Participants will be asked to log any symptoms along with the time and date, type of symptom and whether they were able to record an ECG during the symptoms, in a participant symptom diary. They will return this diary to the local research team along with the participant satisfaction and compliance questionnaire, and smart phone based event recorder at the end of the 90 days. Participants will be phoned at 90 days by the local study team to remind them to complete the participant satisfaction and compliance questionnaire and to return this to the local study team with the symptom diary and smart phone based event recorder. The compliance questionnaire is designed to capture whether participants had the device with them and were able to record a heart tracing during symptoms. Detail the specific study assessments to be performed and the time points during the study - split by visit number if appropriate for clarity. It may be appropriate to prepare a table of assessments by visit.

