## ***5. General Considerations***

### **5.1. Overall**

For all analyses, unless otherwise specified, participants shall be analysed according to treatment received, irrespective of the treatment group they were allocated to, with the exception of AE/SAEs. An additional table will be provided on whether the participant took part in the study and if they did not then their AE/SAEs will be included as part of the control group.

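### SAP 6.4 item 5 plans a between-arm test of monitor compliance, and of satisfaction with the monitor, though only the study arm has a monitor

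*SAP*

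**What the plan says.** **The planned analysis.** SAP 6.4 item 5 has two sentences. The first reads "Participant satisfaction questionnaire responses shall be compared between study arms using" one or more chi-square tests, with a test for trend where suitable. The second reads "A similar analysis shall be performed for participant compliance questionnaire responses". Item 5 plans nothing else for this endpoint, which SAP 2.2 lists as "Participant satisfaction and monitor compliance".

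**Who has the device.** Protocol 6.2 states "All STUDY arm participants will be given an AliveCor Heart Monitor", and adds that the control arm gets no further intervention.

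**Who is asked.** SAP 4.2.2 states "Study arm participants will also be asked about satisfaction and compliance with the heart monitor". The matching sentence in Protocol 6.2 says only that participants will be asked, without naming an arm. Both documents also have participants in both groups complete a standardised written questionnaire, whose items are not given.

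**What is asked.** SAP 4.2.3 explains: "The compliance questionnaire is designed to capture whether participants had the device with them and were able to record a heart tracing during symptoms". Participants also note "whether they were able to record an ECG during the symptoms, in a participant symptom diary".

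**The objective.** Secondary objective 5 in Protocol 2.1.2 is to investigate satisfaction and monitor compliance. It names no comparator.

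**The concern.** A between-arm test needs a response that both arms can give. Compliance with a monitor is defined only for people who have one, and by design the control arm does not. The SAP limits the monitor questions to one arm in 4.2.2 and then, in 6.4, plans a two-arm test on the answers.

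Satisfaction is affected too. SAP 4.2.2 restricts satisfaction with the monitor to the study arm in the same sentence as compliance. The first sentence of item 5 therefore has the same fault for any satisfaction item about the device.

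At stake is whether this part of secondary endpoint 5 has a usable prespecified analysis. As written it does not, and choices such as the denominator are left until the data are in hand. For a recorder that works only when the patient triggers it, readers will want to know how often participants had it with them and managed to use it.

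**Working it through.** The plan states no figure for this endpoint, so there is none to reproduce. The check sets the sections side by side and then asks what the test would do.

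**Step 1: what the second sentence of item 5 refers to.** The only analysis just before it is the between-arm chi-square for satisfaction. Two readings are possible:
- *Between-arm chi-square.* This is the natural reading, because it is the analysis to which compliance is said to be similar.
- *Chi-square without an arm comparison.* Item 5 then names no groups to compare, so the analysis is unspecified.

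The sentence needs correcting on either reading.

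**Step 2: whether controls can supply responses.**

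| Question | Source | Answer |
|---|---|---|
| Who receives a monitor? | Protocol 6.2 | Study arm |
| Who is asked about satisfaction and compliance with it? | SAP 4.2.2 | Study arm |
| Same question in the protocol | Protocol 6.2 | Participants, arm not named, but about the monitor |
| What does the compliance questionnaire cover? | SAP 4.2.3 | Having the device to hand and recording with it |
| What comes back with the questionnaire at 90 days? | SAP 4.2.3 | Symptom diary and event recorder |

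The last row helps with the unrestricted wording. SAP 4.2.3 says participants without naming an arm, yet has them return the recorder with the form, which only someone given a recorder can do.

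**Step 3: what the test would do.** In a chi-square test the expected count in a cell is E = (row total × column total) / grand total, and the statistic is the sum of (O − E)² / E.
- *Controls give no responses.* Take any split in the study arm, for example 80 and 41 out of 121 (an arbitrary split). The control row total is 0, so its expected counts are 0 × 80 / 121 = 0 and 0 × 41 / 121 = 0. Each control cell contributes 0/0, and the statistic is undefined.
- *Controls are sent the form.* Their answer to having the device with them is fixed by the design. A difference between arms then restates allocation and says nothing about compliance.

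**Step 4: whether the default analysis set helps.** Under SAP 5.1, unless otherwise specified, "participants shall be analysed according to treatment received, irrespective of the treatment group they were allocated to". Regrouping in this way still leaves a comparison group without monitors, so the test remains empty.

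**Step 5: what a study-arm summary would deliver.** The documents give no compliance rate, so 50%, 70% and 90% are assumptions. The arm sizes are 121 (randomised per arm) and 110 (before the dropout allowance), both from Protocol 5.5.1 and 8.1. The Wilson 95% interval is

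[p + z²/(2n) ± z·√(p(1 − p)/n + z²/(4n²))] / (1 + z²/n), with z = 1.96.

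For 85/121, p = 0.7025, z²/(2n) = 0.0159, the root term times z is 0.0830, and the divisor is 1.0317. The limits are (0.7184 − 0.0830)/1.0317 = 61.6% and (0.7184 + 0.0830)/1.0317 = 77.7%.

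| Assumed rate | n = 121 | n = 110 |
|---|---|---|
| about 50% | 60/121: 40.8% to 58.4% | 55/110: 40.8% to 59.2% |
| about 70% | 85/121: 61.6% to 77.7% | 77/110: 60.9% to 77.8% |
| about 90% | 109/121: 83.5% to 94.2% | 99/110: 83.0% to 94.3% |

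A one-arm summary is thus informative to within about 5 to 9 percentage points either side if nearly all forms come back. Intervals widen as returns fall.

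**The case against.** **The form has not been seen.** Both arms complete a standardised written questionnaire, and Protocol 6.2 does not limit the monitor questions to one arm. Some satisfaction items may concern care in general and be answered by everyone. This stands for satisfaction, so a reader who infers that the whole satisfaction comparison is invalid goes further than the documents allow. It does not rescue compliance, whose described content has no meaning without a device.

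**An analyst would simply tabulate the study arm.** Probably so, and this is why the point is small. But the SAP is where that choice and its denominator should be fixed.

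**A false positive might be feared.** A reader might infer that the trial would report a spurious significant difference in compliance, with controls counted as non-compliant. The documents do not support this. No section plans to code controls that way, and SAP 5.1.2 rules out imputation. On the text, the likelier outcome is that there are no control responses and the test cannot be run.

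**The endpoint wording might seem to settle it.** A reader might argue that endpoint 5 is not comparative because it omits any reference to standard care. That proves nothing: endpoints 6 and 7 omit it too, yet objectives 6 and 7 are comparisons and the SAP analyses them as such. The sounder support is in Protocol 2.1.2, where objective 5 is the only one of the seven secondary objectives that names no comparator.

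**Conclusion.** The point holds. As naturally read, SAP 6.4 item 5 orders a between-arm test of compliance responses that the control arm cannot meaningfully give, and of satisfaction responses as far as they concern the monitor. SAP 6.4 conflicts here with SAP 4.2.2 and 4.2.3 and with Protocol 6.2.

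The size is modest. Only secondary endpoint 5 is affected; no sample size, error rate or other endpoint changes. It should be corrected, but it does not threaten the trial's main conclusions.

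For compliance, the conclusion rests on the device-specific description in SAP 4.2.3 being a fair account of the form. For satisfaction, it covers only items about the monitor; which items those are has to be read from the form.

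**What to change.** Replace the second sentence of SAP 6.4 item 5 with:

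> Compliance questionnaire responses, and satisfaction items about the monitor, will be summarised as n (%) with 95% CI among participants allocated to the study arm who returned the questionnaire, with the return rate out of all allocated to that arm; no between-arm test will be done.

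In the first sentence, keep the between-arm chi-square only for satisfaction items that both arms answer, if any, and list them.

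Defining the group by allocation departs from the SAP 5.1 default, which permits exceptions where specified. It keeps anyone allocated a monitor who never took it in the base of the return rate.

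The cost is one or two sentences of SAP text and a check of the existing questionnaire for items common to both arms. The study-arm summary needs no data beyond what SAP 4.2.2 and 4.2.3 already plan to collect.

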#### **2.1.2 Secondary Objectives**

1. To investigate the symptomatic rhythm detection rate for cardiac arrhythmia detection at 90 days of a smart phone based event recorder compared to standard care for participants presenting to the ED with palpitations and pre-syncope
2. To compare the time to detection of symptomatic rhythm versus standard care
3. To compare the time to detection of cardiac arrhythmia versus standard care
4. To compare the number of participants treated or (planned for treatment) for cardiac arrhythmia versus standard care
5. To investigate participant satisfaction and monitor compliance
6. To compare the cost of symptomatic rhythm detection at 90 days of a smart phone based event recorder compared to standard care for participants presenting to the ED with palpitations and pre-syncope
7. To compare serious outcomes at 90 days in participants using a smart phone based event recorder compared to standard care

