## **6 STUDY ASSESSMENTS**

### **6.1 SAFETY ASSESSMENTS**

This study has been risk assessed by the Medical Physics and Infection Control teams at the Royal Infirmary of Edinburgh. An Infection Control agreed SOP for cleaning the AliveCor Heart Monitor Device prior to re-use is included in the study paperwork.

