## **8 STATISTICS AND DATA ANALYSIS**

### **8.1 SAMPLE SIZE CALCULATION**

Using a symptomatic rhythm detection rate at 90 days of 25% [3] versus standard care (10%) we estimate 110 participants in each group would have 80% power to determine a 15% improvement in symptomatic rhythm detection. We will recruit an extra 10% in each arm to allow for drop out (i.e. 121 participants in each arm). Our ED sees around 500 eligible participants a year. Assuming a 50% recruitment rate we estimate we will need to recruit for 15 months.

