#### **5.1.2. Missing data**

No imputation for missing data shall be performed. The primary outcome analysis will only be performed on those participants with 90 day follow up, however a table to data completeness shall be provided which will capture any participants who were lost to follow-up.

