### **6.3. Primary outcome**

The baseline to 90 day change in diagnostic yield (i.e. presence/absence symptomatic rhythm detection) of a smart phone based event recorder compared with standard care only shall be analysed using a comparison of proportions test.

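### SAP 6.4 item 6 tests cost-effectiveness with a two-sample t-test or rank test; on the natural reading this compares cost per participant alone and does not deliver secondary endpoint 6

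*SAP*

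**What the plan says.** Protocol 2.1.2, objective 6, is: "To compare the cost of symptomatic rhythm detection at 90 days of a smart phone based event recorder compared to standard care". Secondary endpoint 6, in Protocol 2.1.4 and SAP 2.2, is labelled only as a cost-effectiveness analysis.

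SAP 6.4 item 6 first compares five counts of resource use between arms. It then says: "A comparison of the overall cost-effectiveness of the smart phone based event recorder and standard care shall be provided using a two-sample t-test", with a non-parametric equivalent as the alternative. The data for that comparison are described in one sentence: "The costing scope will include primary care, secondary care and community NHS costs which shall be provided separately by the CI for analysis".

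Detection is analysed elsewhere. SAP 6.3 treats it as a yes/no outcome for each participant ("presence/absence symptomatic rhythm detection") and compares proportions. Neither document links cost to detection. Neither defines an effect measure, a cost per detection, an incremental ratio, a value placed on a detection, or an interval for any of these.

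**The concern.** A t-test or rank test compares a quantity that every participant has. Cost per detection is not such a quantity. It is a ratio formed at arm level, and it is undefined for a participant with no detection, which at the planning rates is 75% of the study arm and 90% of the control arm. The one per-participant variable that the SAP supplies here is cost, so that is what would be tested.

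The result could then be reported as the cost-effectiveness finding although it carries no information on detection. The device is expected to raise detection, so a strategy that costs more per participant may still cost less per rhythm detected. A cost test cannot show this, and it gives no measure of how precisely the cost of a detection is known.

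The non-parametric alternative adds a second problem. It compares ranks, whereas the numerator of any cost-effectiveness ratio is a difference in arithmetic means.

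**Working it through.** **Inputs.** Protocol 8.1 gives detection of 25% (study) and 10% (control), with 110 per arm before the drop-out allowance and 121 after. The documents give no costs, so results are in units of C, the mean cost per control participant. Write r for the ratio of study to control mean cost; r is an assumption and is varied.

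**The plan's own figure.** Protocol 8.1 states: "we estimate 110 participants in each group would have 80% power to determine a 15% improvement in symptomatic rhythm detection". Alpha is not stated. At an assumed two-sided 5%, the normal-approximation formula gives 100 per arm, or 113 with continuity correction; power at 110 is 83.8% without correction. The figure of 110 is thus reproduced to within 3% by the corrected formula, and 110 × 1.10 = 121. This point does not depend on it.

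**Cost per detection against mean cost.**
- Cost per detection in an arm = mean cost / detection proportion. Study: rC/0.25 = 4rC. Control: C/0.10 = 10C.
- Cost per additional detection = (rC − C)/(0.25 − 0.10) = (r − 1)C/0.15.

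| r | Difference in mean cost | Cost per detection, study | Cost per detection, control | Cost per additional detection |
|---|---|---|---|---|
| 1.0 | 0 | 4C | 10C | 0 |
| 1.5 | 0.5C | 6C | 10C | 3.3C |
| 2.0 | 1.0C | 8C | 10C | 6.7C |
| 2.5 | 1.5C | 10C | 10C | 10C |
| 3.0 | 2.0C | 12C | 10C | 13.3C |

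The two comparisons agree on the costlier arm only when r is below 1 (in a different sense: the study arm is then cheaper on both) or above 2.5. Between 1 and 2.5 they point in opposite directions. Whether the cost test reaches significance depends on the spread of costs. With r = 1.5, 110 per arm and an assumed common SD of C, its power is 96%; with an SD of 2C it is 46%.

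**Why an interval is needed.**
- SE of the detection difference = sqrt(0.25×0.75/110 + 0.10×0.90/110) = 0.0502.
- 95% interval: 0.15 ± 1.96 × 0.0502 = 0.0516 to 0.2484.
- The multiplier applied to the cost difference is 1/0.15 = 6.67, with a range of 1/0.2484 = 4.0 to 1/0.0516 = 19.4 from detection alone. With 121 per arm the range is 4.1 to 17.8.
- At equal mean costs, the ratio of control to study cost per detection is 10/4 = 2.5. Its log-scale SE is sqrt(0.75/27.5 + 0.90/11) = 0.330, which gives 1.3 to 4.8.
- The detection interval would include zero in about 15% of trials: 0.15/0.0502 = 2.99; 2.99 − 1.96 = 1.03; 1 − Φ(1.03) = 0.15. A simulation of 20,000 trials also gave 15%. In those trials an interval for the incremental ratio is not interpretable, so the joint distribution of the two differences should be shown as well.

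These widths describe how imprecise the ratio is. They are not a measure of the defect, and better analysis wording does not shrink them.

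**The rank alternative.** Suppose study-arm participants carry a flat cost and, on average, equally lower other costs, so that the means are equal. The flat cost lifts every low-cost study participant above the low-cost controls. A rank test can then reject although the mean difference is zero. How often depends heavily on the cost distribution, which the documents do not give, so no rate is quoted.

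**The case against.** - **Objective 6 can be read loosely**, as the cost of each care strategy. A comparison of mean costs then answers part of it. This stands, and it is why the point rests mainly on endpoint 6, which asks for cost-effectiveness and not for cost alone.
- **The pieces are all there.** Detection proportions come from SAP 6.3 and mean costs would come from item 6, so point estimates of cost per detection follow by division. This also stands. A reader might infer that the trial cannot yield a cost per detection; the documents do not support that. The gap is that no ratio is pre-specified and no interval is planned.
- **Net benefit is a per-participant quantity and can be t-tested.** True, but it needs a value per detection, and neither document gives one.
- **The test could be limited to participants with a detection.** That would select on an outcome after randomisation (about 27.5 versus 11 of 110 per arm) and leave out the cost of everyone else, so it would not answer the objective.
- **The 2.5-fold gap at equal costs is only 25%/10%**, which the primary analysis already tests. Fair: it illustrates what a cost test leaves out and is not a separate effect.
- **Device costs.** A reader might infer that the costing leaves out the device, training and ECG review. The SAP is silent on these and does not exclude them. Protocol 6.1 shows that devices are re-used ("An Infection Control agreed SOP for cleaning the AliveCor Heart Monitor Device prior to re-use is included in the study paperwork"), but what to count is a costing choice that the SAP leaves to the chief investigator.

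**Conclusion.** The point holds, as a mismatch between a named secondary endpoint and the method given for it. Followed as written, item 6 most naturally yields a test of cost per participant. That does not deliver endpoint 6 and answers objective 6 at most in part. At the planning rates it would miss a 4C versus 10C contrast when mean costs are equal, and it would point the opposite way from cost per detection for any cost ratio between 1 and 2.5.

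This rests on two things: the natural reading of item 6, since the SAP never says which variable is tested, and the planning detection rates. The size of any real discrepancy depends on costs that the documents do not give.

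Two stronger conclusions are not supported. The rank test cannot be assigned a particular false-positive rate, because that turns on the unknown cost distribution. Nothing here touches the primary analysis, the sample size or the other secondary endpoints. The change is worth making because the endpoint is pre-specified in both documents and the remedy is cheap.

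**What to change.** Keep the costing-scope sentence in SAP 6.4 item 6 unchanged. Replace the test sentence before it with:

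> Mean 90-day NHS cost per participant, within the costing scope below, will be compared between study arms as a difference in arithmetic means with a bootstrap 95% CI; no rank test will be used for cost. The effect measure is symptomatic rhythm detection at 90 days. Mean cost per detection in each arm and the difference in mean cost divided by the difference in detection proportion will be reported. Uncertainty will come from resampling cost and detection jointly within arm, in participants with 90-day follow-up and cost data, and the joint distribution of the cost and detection differences will always be shown; the number excluded will be given by arm.

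Optionally, the chief investigator states before database lock whether device, training and ECG review costs are included.

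The cost is SAP wording, a bootstrap and possibly a wide interval for the ratio. Two practical points follow:
- Nothing is imputed, the primary set is already limited ("The primary outcome analysis will only be performed on those participants with 90 day follow up"), and GP contacts are collected by telephone ("Number of GP presentations due to palpitations/pre-syncope (via phone follow-up)"). The cost set may therefore be smaller than the primary set, which is why exclusions are counted by arm.
- Community costs are in scope but have no matching count in item 6, so their source needs to be stated.

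Protocol 8.2 specifies intention to treat and SAP 5.1 specifies treatment received. That is a separate point, to be reconciled once for all analyses.
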